Separately, 10 endoscopists (6 novice and 4 expert) will be asked to interpret a selection of the HRME images. The novices will include current GI fellows at BCM and novice endoscopists on the protocol, while the expert endoscopists will be experienced endoscopists listed on the protocol. The 10 subjects will receive information about the procedures verbally as a waiver of documentation of consent is requested. Each of the subjects will first receive training using a training set, and then will be evaluated using a testing set of images. They will be asked to give a read (neoplastic or non-neoplastic) and then to provide their confidence level (high or low) for each image determination. Following the subjective HRME image read, each image will be evaluated using the automated software algorithm, with the subjective and automated reads being blinded to each other, as well as to the gold standard consensus pathology read by 2 expert GI pathologists. The subjective reads will be compared to the automated reads and the consensus pathology reads.

Subjects at the Jilin site will be asked to complete a survey addressing barriers to esophageal cancer screenings. Subjects will be asked about beliefs and attitudes surrounding screening techniques.

Section G: Sample Size/Data Analysis

G1. Sample Size

How many subjects (or specimens, or charts) will be used in this study?

Local: 300 Worldwide: 1300

Please indicate why you chose the sample size proposed:

This is an IRB revision and will NOT change our proposed sample size. Rather, in the remaining patients to be accrued, we will determine the accuracy of our revised (AR platform). Thus, the goals and sample size of the original trial will remain intact which is to compare LCE to LCE+HRME (subjective read).

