For the HRME image interpretation study, the sample size of 10 endoscopists was selected based on a prior power analysis based on non-inferiority. The 10 endoscopists will review about 140 HRME images. It is hypothesized that software interpretation of the HRME images will be non-inferior to the endoscopist interpretation. Non-inferiority is defined as a 10% difference in specificity between the two groups with 90% power and alpha of 0.05.

G2. Data Analysis

Provide a description of your plan for data analysis. State the types of comparisons you plan (e.g. comparison of means, comparison of proportions, regressions, analysis of variance). Which is the PRIMARY comparison/analysis? How will the analyses proposed relate to the primary purposes of your study?

Among the surveillance group, three analyses in testing the null hypotheses will be performed, including two interim analyses and one final analysis. The analysis will be performed when 220, 440 and 650 study subjects have been accrued, respectively.

The interim analysis will use a symmetric two sided group sequential design using a Hwang-Shih-DeCani spending function with beta spending of .4, which provides an O'Brien-Fleming-like conservative upper bound. This approach requires a two sided significance level of 0.0026 and 0.0114 for the interim analysis and 0.0464 for the final analysis of overall survival.

There will be no interim analysis for the screening population.

The primary analysis for the surveillance group is to test non-inferiority in sensitivity and superiority in specificity of LCE+HRME vs. LCE alone. The test statistic is based on the formula in Pepe (Chapter 8, The statistical Evaluation of Medical Tests for Classification and Prediction, 2003). Additionally, sensitivity and specificity of LCE+HRME vs. LCE alone will be estimated on a per patient basis with 95% confidence intervals. The primary goal for the screening group is to test whether the negative predictive value (NPV) of LCE+HRME is higher than LCE alone. This is done using Fisher's exact test. Additionally, the negative predictive value will be summarized with 95% confidence intervals.

The secondary analysis includes diagnostic yield, clinical efficiency, clinical impact, progression rate, and the rate of adverse events.

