Among the HRME image interpretation study, the sensitivity, specificity, and accuracy for all participants, as well as novice vs. endoscopist participants, will be tabulated. Interrater reliability among all endoscopists and the level of agreement between the endoscopists and the automated software will be calculated using Kappa statistic.

Section H: Potential Risks/Discomforts

H1. Potential Risks/Discomforts

Describe and assess any potential risks/discomforts; (physical, psychological, social, legal, or other) and assess the likelihood and seriousness of such risks:

Possible risks associated with the study procedures are listed below. There may also be risks that are not known.

Many side effects go away soon after the procedure, but in some cases, side effects may be serious, long-lasting or permanent, and may even cause death. It is important that the participant tell the study staff about any side effects that he/she may have had even if he/she does not think it is related to the procedure.

Allergic reaction (anaphylaxis) There is the possibility of a severe allergic reaction to the Proflavine contrast dye in which participant may have difficulty breathing and the blood pressure may drop. There are procedures in place to treat participant in endoscopy room in the event that this happens.

Specimen Imaging Probe There are no known risks from the use of the imaging probe.

Anesthesia There may be additional risks from the added time of additional sedation, such as decreased blood pressure.

Aspiration (inhaling) of fluid into the lungs during endoscopy This might cause inflammation in the lungs. Safeguards to prevent this from happening while the participant is under anesthesia will be in place during and after the procedure, and participant's breathing and other vital signs will be carefully monitored.

If participant experience any symptoms other than those that the study doctor has informed the participant are associated with the procedure, please let the study doctor know.

Pregnancy Insufficient information is available on the use of Proflavine in pregnancy. Drugs can have harmful effects on the fetus at any stage of pregnancy.

Loss of Privacy

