When research is conducted in collaboration with outside entities or organizations, the PI must obtain the necessary approvals from those entities. The BCM IRB may request documentation that such approvals have been obtained. Please list and describe the planned sites for this multi-site research for which the BCM PI is either Sponsor-Investigator and/or Coordinating Center. Sites that do not meet the requirements for inclusion in section A6a of the protocol summary and BCM informed consent documents should be listed here.

Baylor College of Medicine, Texas, USA Cancer Institute, Chinese Academy of Medical Sciences (CICAMS), Beijing, China The First Hospital of Jilin University, Changchun, Jilin, China National Cancer Institute Rice University, Texas, USA Harvard University School of Medicine, MA, USA

Section I: Potential Benefits

Describe potential benefit(s) to be gained by the individual subject as a result of participating in the planned work.

There may not be any benefit to participants from taking part in this research.

Describe potential benefit(s) to society of the planned work.

Participation in this study may help future patients with esophageal squamous cell cancer from what is learned in this study.

For the post hoc image analysis project, the benefit to society may be the introduction of an innovative, low cost screening technology for esophageal squamous cell carcinoma. Utilizing a reliable, automated HRME image interpretation could reduce the need for endoscopists trained in HRME, and allow for use of the HRME device in resource poor areas and countries. Have a real-time technology that aids in decision making may result in reduced biopsies, decreased costs, and help facilitate immediate treatment.

Do anticipated benefits outweigh potential risks? Discuss the risk-to-benefit ratio.

The incremental risks of HRME with proflavine, added to the SOC white light with ILugol's iodine are minimal. White light endoscopy is standard of care and all subjects will be undergoing this SOC procedure.

Section J: Consent Procedures

J1. Waiver of Consent

Will any portion of this research require a waiver of consent and authorization?

Yes

Please describe the portion of the research for which a waiver is required. (Example: chart review to determine subject eligibility)

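### The image-reading sub-study defines non-inferiority of the software by specificity alone, so software that gains specificity by under-calling neoplasia could meet the definition

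*Combined protocol and SAP*

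**What the plan says.** The hypothesis of the image interpretation sub-study, in G1 (Sample Size), is general: "It is hypothesized that software interpretation of the HRME images will be non-inferior to the endoscopist interpretation". The criterion that follows is not: "Non-inferiority is defined as a 10% difference in specificity between the two groups with 90% power and alpha of 0.05". On size, G1 says "The 10 endoscopists will review about 140 HRME images", and F2 (Procedure) describes the readers as 6 novices and 4 experts. The split of the images into neoplastic and non-neoplastic, the assumed specificity, the sidedness of alpha and the handling of the same images being read by all readers and by the software are not given.

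For this sub-study, G2 (Data Analysis) says that "the sensitivity, specificity, and accuracy for all participants, as well as novice vs. endoscopist participants, will be tabulated", and that "the level of agreement between the endoscopists and the automated software will be calculated using Kappa statistic". It names no non-inferiority test, no sensitivity margin and no minimum sensitivity or kappa. F2 adds that subjective reads will be compared with the automated reads and with consensus pathology, again without a criterion.

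For the surveillance group of the main trial, G1 and G2 do pair the two measures: non-inferiority in sensitivity together with superiority in specificity.

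**The concern.** The hypothesis concerns interpretation as a whole, while the criterion covers only half of it. Each read is a two-way call, neoplastic or not. Moving calls from neoplastic to non-neoplastic can only raise or preserve specificity, and can only lower or preserve sensitivity. A specificity-only definition therefore cannot fail software for missing neoplasia, and it becomes easier to meet the more the software under-calls.

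Section I (Potential Benefits) gives the hoped-for benefit: "Utilizing a reliable, automated HRME image interpretation could reduce the need for endoscopists trained in HRME". A finding of non-inferiority that leaves sensitivity out would be weak support for that. What is at stake is what the sub-study may conclude about the software.

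**Working it through.** **Inputs from the documents.** Margin 10 points on specificity, power 90%, alpha 0.05, about 140 images, 10 readers (all G1). The pilot HRME specificity is 79% (Section D).

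**Assumptions.** Reader specificity 79%, borrowed from the pilot because G1 states none; reader sensitivity 95%; 70 benign and 70 neoplastic images; one reader against the software, treated as independent samples; a Wald confidence bound at one-sided 0.05 unless stated otherwise.

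**1. The stated 90% power.** For equal true specificity p, unpaired, n per group = (1.645 + 1.282)² × 2p(1−p) / 0.10², with (1.645 + 1.282)² ≈ 8.564.
- p = 0.79: 8.564 × 2 × 0.79 × 0.21 / 0.01 ≈ 284.1, so 285 benign images.
- p = 0.90: 155. p = 0.95: 82.
- At one-sided 0.025 the three figures are 349, 190 and 100.
- Paired, n = 8.564 × discordance / 0.10²: 86 at 10% discordance and 172 at 20%.

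In the unpaired calculation, 140 images give 90% power only if all are benign and specificity is at least about 0.91; in the paired one, only if discordance is low. The 90% can be neither reproduced nor refuted from what is stated.

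**2. The limiting case.** Software that calls every image non-neoplastic has specificity 1, so its observed specificity cannot be below the readers'. With q the readers' false-positive rate and m benign images, the Wald bound passes if q + 0.10 > 1.645 × √(q(1−q)/m), that is, if m > 2.706 × q(1−q)/(q + 0.10)². The right-hand side is largest at q = 1/12, where it is 2.706 × 2.273 ≈ 6.15. From 7 benign images on, this software passes whatever the readers' specificity.

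**3. Intermediate cases.** The pass probability on specificity is Φ{(software − reader + 0.10)/SE − 1.645}.
- Software 0.90 against readers 0.79, 70 images: SE = √((0.90×0.10 + 0.79×0.21)/70) = 0.0605; 0.21/0.0605 − 1.645 ≈ 1.83; probability about 0.97.
- Sensitivity 0.70 against 0.95 with the same 10-point limit: SE = √((0.70×0.30 + 0.95×0.05)/70) = 0.0607; −0.15/0.0607 − 1.645 ≈ −4.12; probability below 0.1%.
- Equal specificity of 0.79: SE = √(2×0.79×0.21/70) = 0.0688; 0.10/0.0688 − 1.645 ≈ −0.19; probability about 0.42.

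Simulation of the same rule (200,000 runs) gives:

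| Software specificity / sensitivity | Passes on specificity alone | Passes both limits |
|---|---|---|
| 0.79 / 0.95 | 43% | 36% |
| 0.85 / 0.80 | 80% | 0.5% |
| 0.90 / 0.70 | 97% | <0.1% |
| 0.95 / 0.50 | 99.9% | 0% |
| 1.00 / 0.00 | 100% | 0% |

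**4. Dependence on the image split.** Software at 0.90/0.70 passes on specificity alone 80% of the time with 35 benign images (71% at one-sided 0.025) and over 99% with 105.

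**5. Same software, stricter cut-off.** On an assumed equal-variance binormal curve through sensitivity 0.95 and specificity 0.79, moving to specificity 0.95 lowers sensitivity to 0.79, a loss of 16 points. The pass probability on specificity alone rises from 43% to 99.9%.

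**6. Images needed for a 10-point sensitivity limit.** By the formula in step 1, 90% power needs 82 neoplastic images per group at 95% sensitivity or 155 at 90% (100 or 190 at one-sided 0.025).

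**The case against.** The definition stands in a sample-size paragraph, and G2 contains no rule by which non-inferiority would be declared. A reader might infer that the plan commits the sponsor to declaring the software non-inferior on specificity. The documents do not go that far: they define non-inferiority one way and then leave the test unspecified. The definition is nevertheless the only one given.

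A reader might also infer that the plan ignores missed neoplasia. It does not. Sensitivity is a listed output, and software that calls everything benign would show a kappa of zero against any reader who calls some images neoplastic, because observed and chance agreement then coincide. This softens the point without removing it. Neither output has a threshold, and G2 ties the tabulated measures to the participants without naming the software's own sensitivity.

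Specificity has a rationale here, since Section D presents HRME as a way to lower Lugol's false positives. Under F2 all Lugol's-abnormal areas are biopsied anyway, and the sub-study has no consequence for patient care. Section I describes a possible benefit to society and not a claim tied to this test. These arguments limit the weight of the point. They do not explain why a general hypothesis has a one-sided criterion when the surveillance analysis pairs both measures.

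No section describes an adjustable cut-off or tuning on the test images, and F2 blinds the automated reads to pathology and to the subjective reads. The cut-off example shows how the criterion behaves; it does not suggest that anyone would exploit it.

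**Conclusion.** The point holds for the image interpretation sub-study: the definition of non-inferiority omits sensitivity, and nothing else in the plan supplies a sensitivity criterion. The limiting case needs no assumption about reader performance and, under the Wald rule, only a handful of benign images.

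The percentages are illustrations. They rest on assumed performance values, an assumed 70/70 split and an unpaired single-reader approximation, whereas the design has 10 readers and the software on the same images. It would be wrong to infer that any software passes easily: at a specificity equal to the readers' 79% it passes only about 43% of the time with 70 benign images. The easy pass belongs to software that actually gains specificity. The randomized comparison is untouched, so this is a recommended correction to a sub-study.

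**What to change.** Define non-inferiority as meeting both the planned 10-point specificity limit and a pre-stated sensitivity limit (the same 10 points would be one choice) on the same images and reads. No alpha split is needed, because both are required. Enter the test in G2, state the sidedness, and state the numbers of neoplastic and non-neoplastic test images. Recompute the power for the joint claim from stated assumptions that account for the same images being read by 10 readers and the software.

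If about 140 images cannot support both limits, restrict the conclusion to non-inferiority in specificity, and report the software-minus-reader sensitivity difference with its confidence interval beside it.

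The wording change costs little, but power has a price: the joint claim will have less than the stated 90%. Multiplying 0.9 × 0.9 to get 0.81 is not a substitute for the calculation, because the 90% cannot be reproduced and independence and 90% power for sensitivity would both have to be assumed. On the unpaired figures in step 6 of the working, more neoplastic images may be needed.

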Specific information concerning psychiatry notes:

No

Demographic information (name, D.O.B., age, gender, race, etc.):

Yes

Full Social Security #:

No

Partial Social Security # (Last four digits):

No

Billing or financial records:

No

Photographs, videotapes, and/or audiotapes of you:

No

Other:

No

Will additional pertinent information be provided to subjects after participation?

No

If No, explain why providing subjects additional pertinent information after participation is not appropriate.

The information collected would include demographics and relevant clinical data. It would not include any additional information that could not be accessed by the patients through their own review of their medical record.

J1a. Waiver of requirement for written documentation of Consent

Will this research require a waiver of the requirement for written documentation of informed consent?

Yes

Explain how the research involves no more than minimal risk to the participants, and the specifics demonstrating that the research does not involve procedures for which written consent is normally required outside of the research context.

We are requesting a waiver of the requirement for written documentation of informed consent for the small 8 subject study evaluating the HRME image interpretation among novices and fellows only. We are not requesting a waiver for the larger 1300 subject trial. The 8 subject study involves no more than minimal risk to participants as the procedure is limited to completing a training and testing set for image interpretation, either in person or remotely. The procedure will be non invasive and short in duration (less than one hour per subject). The subjects are simply asked to interpret each image as appearing to be neoplastic or non-neoplastic, and then to provide their confidence level (high or low) for each response.

J2. Consent Procedures

Who will recruit subjects for this study?

PI

PI's staff

Describe how research population will be identified, recruitment procedures, any waiting period between informing the prospective participant and obtaining consent, steps taken to minimize the possibility of coercion or undue influence and consent procedures in detail.

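### The image interpretation study is sized for non-inferiority of software to endoscopists in specificity, but no specified analysis sets that difference against the 10% margin

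*Combined protocol and SAP*

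**What the plan says.** Section G1 (Sample Size) gives the sub-study's hypothesis: "It is hypothesized that software interpretation of the HRME images will be non-inferior to the endoscopist interpretation". It says that "the sample size of 10 endoscopists was selected based on a prior power analysis based on non-inferiority", that "The 10 endoscopists will review about 140 HRME images", and sets the criterion: "Non-inferiority is defined as a 10% difference in specificity between the two groups with 90% power and alpha of 0.05". It does not say whether the 10% is absolute or relative, or whether alpha is one-sided or two-sided.

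Section F2 (Procedure) describes the reading: "10 endoscopists (6 novice and 4 expert) will be asked to interpret a selection of the HRME images". Then "each image will be evaluated using the automated software algorithm, with the subjective and automated reads being blinded to each other", and both are blinded to the consensus pathology read. F2 adds that the endoscopists' reads will be compared with the software reads and with pathology, but names no endpoint, method or margin.

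Section G2 (Data Analysis) gives this sub-study two sentences. Sensitivity, specificity and accuracy are to be tabulated for the participants overall and by experience group. Inter-rater reliability is to be assessed, and "the level of agreement between the endoscopists and the automated software will be calculated using Kappa statistic".

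Section J1a (waiver of written documentation of consent) refers to "the small 8 subject study evaluating the HRME image interpretation among novices and fellows only".

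**The concern.** A study sized on a non-inferiority hypothesis needs an analysis that estimates the difference and sets its confidence limit against the margin. G1 supplies the hypothesis, endpoint, margin, power and alpha, but the G2 text for this sub-study stops at tabulation and agreement. The participants are the endoscopists, so even the software's own specificity is not clearly among the planned tabulations.

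At stake is the claim the sub-study exists to support. Section I (Potential Benefits) foresees that reliable automated reading could lessen dependence on HRME-trained endoscopists. That needs the non-inferiority conclusion. If the test, its sidedness and its variance are chosen only after the reads are known, the conclusion is weaker than a prespecified one. The choice of variance matters because every reader and the software assess the same images.

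**Working it through.** **1. Hypothesis and analysis side by side.**

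| Element | Sizing text (G1) | Analysis text (G2, with F2) |
|---|---|---|
| Comparison | Software vs endoscopist | Agreement by kappa; F2 names a comparison without a method |
| Endpoint | Specificity | Participants' specificity tabulated; software's not explicitly |
| Margin | 10% | Not mentioned |
| Alpha, sidedness | 0.05, sidedness not stated | Not mentioned |
| Interval, test or decision rule | Non-inferiority | None |
| Handling of shared images | Not stated | None |

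The non-inferiority test that G2 does specify is for sensitivity in the surveillance group (LCE+HRME vs LCE). It does not cover this sub-study.

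**2. Can kappa stand in?** Assume 140 images, of which 70 are non-neoplastic, and all 70 neoplastic images called positive by both software and reader. On the non-neoplastic images, both are negative on 49, both are positive on 7, and one alone is positive on 14.

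- Case A, the software makes the 14 extra false calls: software specificity 49/70 = 70%, reader (49+14)/70 = 90%.
- Case B, the reader makes them: the two figures swap.
- Observed agreement in both cases: (77+49)/140 = 0.900.
- Chance agreement in both cases: (91×77 + 49×63)/140² = 10,094/19,600 = 0.515.
- Kappa in both cases: (0.900 − 0.515)/(1 − 0.515) = 0.79.

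The same kappa goes with a 20-point deficit (twice the margin) and with a 20-point advantage.

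**3. Can the stated size be reproduced?** No. The documents do not give the number of non-neoplastic images, the expected specificities, the reader-software discordance, the between-reader variation or the sidedness. The following is illustrative only, with a true difference of zero and an absolute margin of 0.10.

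One reader vs software, paired, with discordance d on non-neoplastic images: n = d(z₁₋α + z₀.₉₀)²/0.10². One-sided alpha 0.05 gives (1.6449 + 1.2816)² = 8.564.

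- d = 0.10: n = 85.6, so 86.
- d = 0.20: n = 171.3, so 172.
- At one-sided 0.025 the figures are 106 and 211.

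Software vs the average of 10 readers: assume specificity p = 0.85 for all, pairwise discordance 0.20, fixed readers and inter-reader correlation ρ. Then p(1−p) = 0.1275, the software-reader covariance is 0.1275 − 0.20/2 = 0.0275, and the variance per image is 0.1275(1 + 0.1 + 0.9ρ) − 2×0.0275.

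| ρ | Variance per image | n at one-sided 0.05 |
|---|---|---|
| 0.2 | 0.108 | 93 |
| 0.4 | 0.131 | 113 |
| 0.6 | 0.154 | 132 |

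Treating readers as random would raise these figures. Across these assumptions the need runs from 86 to 172 non-neoplastic images at one-sided 0.05. About 140 images in total might or might not be enough.

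**4. Why the variance must be named.** The software gives one read per image. With 70 non-neoplastic images (assumed) and specificity 79% (the pilot HRME figure in Section D), its standard error is √(0.79×0.21/70) = 4.9 points. Counting that read once per reader, as 700 independent reads, would give √(0.79×0.21/700) = 1.5 points. The plan does not propose this. It simply leaves the method open.

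**The case against.** Much of the frame is fixed. G1 sets the endpoint, margin, power and alpha, and F2 sets blinded reads and consensus pathology as the reference. The software reads will exist, so the specificity difference can be computed. Kappa is used in its normal role, to describe agreement, and is never offered as the non-inferiority test. This is a small reader sub-study. All of that stands. The gap is that no test is specified, not that none could ever be done.

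A reader might infer three stronger things.

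- **That the sub-study is underpowered.** The documents do not show this. The power analysis that G1 cites is not included. Single-reader figures rest on assumed inputs and do not match a reader-average comparison, which can need fewer images.
- **That the reads will be pooled as if independent.** No section says so, and G2 uses a correlated-data model for biopsies in the main trial. That recognises clustering elsewhere, but it supplies no method here.
- **That the reader number is uncertain for the analysis.** F1 (Inclusion Criteria), F2 and G1 all give 10. Only J1a says 8, and F2 itself ties the consent waiver to the 10 readers. This is a clerical conflict.

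**Conclusion.** The point holds as a mismatch between hypothesis and analysis. The image study is sized on non-inferiority in specificity, and no specified analysis sets the software-minus-endoscopist difference against the 10% margin. As written, the plan does not yield the conclusion it was sized for. This rests on the text alone and on no assumed figure.

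The kappa example (0.79 in both directions) is an illustration of why agreement cannot substitute. The image counts of 86 to 172 are likewise illustrative: they show that the 90% power cannot be checked, not that it is wrong. The trial's primary comparisons in the surveillance and screening groups are not affected.

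**What to change.** In G2, add for the image interpretation study:

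- **Primary analysis:** the specificity difference, software minus reader average, on images that are non-neoplastic by consensus pathology.
- **Decision rule:** non-inferiority is declared if the lower confidence limit is above −10 percentage points. State the sidedness of the 0.05 alpha and that the margin is absolute.
- **Variance:** a method that accounts for all readers and the software reading the same images, for example a multi-reader multi-case analysis or a bootstrap over images and readers.
- **Descriptive results:** tabulate the software's own sensitivity, specificity and accuracy beside the readers', and keep kappa as a description of agreement.

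In G1, state the non-neoplastic image count, the expected specificities, and the discordance and reader-variation assumptions behind the 90% power.

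Separately, as an administrative correction, reconcile the J1a wording on reader number and type with F1, F2 and G1.

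The cost is a few sentences and a little analysis work. No new patients or procedures are needed.

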Sample Size Calculation (This has NOT changed from original IRB): The sample sizes are calculated separately for the two risk groups (650 in surveillance group and 650 in screening group). Among the surveillance group, we want to test non-inferiority in sensitivity and superiority in specificity of LCE+HRME vs. LCE alone. The standard endoscopic evaluation using LCE has high sensitivity of about 95% but with low specificity at about 65%. Based on the preliminary data, we hypothesize that LCE+HRME has the sensitivity of at least 90% level, which is similar to that of LCE, but LCE+HRME would improve the specificity to 85%. With significance level of 0.05 and 80% power, we need 223 neoplastic patients and 65 benign patients in each arm (LCE and LCE+HRME) to conclude that LCE+HRME has similar sensitivity as LCE alone and had higher specificity than LCE alone. Hence, we need 446 neoplastic patients and 130 benign patients. The sample size calculation is based on the formula in Pepe (Chapter 8, The statistical Evaluation of Medical Tests for Classification and Prediction, 2003).

According to the preliminary results, greater than 80% patients in the surveillance group would have neoplasia. We anticipate the enrollment of total 650 patients in the surveillance group to ensure the accrual of 446 neoplastic patients and 130 benign patients.

In screening group, we will study the accuracy of LCE+HRME for the diagnosis of neoplasia, and test whether the negative predictive value (NPV) of LCE+HRME is higher than LCE alone. The NPV for using LCE alone is about 95%. We hypothesize that the NPV for LCE+HRME should be at least 99% to be useful. A sample of 300 per arm would provide 82.1% power for this hypothesis with a 5% type-I error. Assuming an 8% loss to follow-up or incomplete data, we need to recruit 325 subjects per arm in the screening population.

Power Calculation (Augmented Reality HRME Revision): We anticipate having at least 400-500 subjects remaining by the time the Augmented Reality HRME revision IRB is approved and funding from the NCI obtained. With 400 patient Augmented Reality HRME data, assuming an accuracy of 83% AND 650 LC patient, assuming an accuracy of 57%, the study should have >93% power to detect a statistically significant difference with an alpha error rate of 0.05.

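### The surveillance group's interim rule is attached to an endpoint the trial does not have, its spending parameter and printed levels disagree, and its sidedness appears not to match the sample size.

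*Combined protocol and SAP*

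**What the plan says.** Section G2 (Data Analysis) plans two interim analyses and one final analysis in the surveillance group: "The analysis will be performed when 220, 440 and 650 study subjects have been accrued, respectively". The design is "a symmetric two sided group sequential design", built "using a Hwang-Shih-DeCani spending function with beta spending of .4", and is described as giving a conservative bound of O'Brien-Fleming type. The thresholds are "a two sided significance level of 0.0026 and 0.0114 for the interim analysis and 0.0464 for the final analysis of overall survival".

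Later in the same section: "The primary analysis for the surveillance group is to test non-inferiority in sensitivity and superiority in specificity". The secondary list reads: "The secondary analysis includes diagnostic yield, clinical efficiency, clinical impact, progression rate, and the rate of adverse events".

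Section G1 (Sample Size) uses a significance level of 0.05, with no sidedness given, and 80% power. It arrives at 223 neoplastic and 65 benign patients per arm. It plans 650 enrolled "to ensure the accrual of 446 neoplastic patients and 130 benign patients", on the expectation that "greater than 80% patients in the surveillance group would have neoplasia".

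**The concern.** This paragraph sets the thresholds for the surveillance group's primary tests at all three looks. Four of its elements do not fit.

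- **Endpoint.** The final level is assigned to overall survival, which the plan does not measure.
- **Parameter.** The spending parameter as it reads cannot produce the printed levels or the described shape.
- **Label.** Beta spending normally governs a futility bound. None is printed, and the design is called symmetric and two-sided.
- **Sidedness.** The levels are two-sided, while the sample size appears to be one-sided.

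The first three leave a pre-specified decision rule that cannot be traced to its own specification. The fourth affects power: if the sizes are one-sided, the surveillance tests have clearly less than the stated 80%.

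**Working it through.** **1. Endpoint.** Section D lists efficiency, clinical impact, performance characteristics and cost-effectiveness. The G2 primary analyses are sensitivity and specificity (surveillance) and negative predictive value (screening). The G2 secondary list has no survival item. Follow-up in F2 and G2 concerns progression of neoplasia. Overall survival appears only in the interim paragraph.

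**2. Parameter against printed levels.** Inputs: looks at 220, 440 and 650 (G2), so t = 0.3385, 0.6769 and 1 if information is proportional to accrual; total 0.05, taken as two-sided to match the rule. The Hwang-Shih-DeCani function is α(t) = 0.05(1 − e^(−γt))/(1 − e^(−γ)). At look 1 the nominal level equals the amount spent:

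- γ = 0.4: 0.05 × (1 − 0.8734)/(1 − 0.6703) = 0.0192
- γ = −4: 0.05 × (3.872 − 1)/(54.60 − 1) = 0.0027

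Later levels come from recursive integration of the joint null distribution:

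| Source | Look 1 | Look 2 | Final |
|---|---|---|---|
| Printed | 0.0026 | 0.0114 | 0.0464 |
| γ = 0.4 | 0.0192 | 0.0225 | 0.0250 |
| γ = −4 | 0.0027 | 0.0114 | 0.0455 |
| γ = −4.5 | 0.0020 | 0.0100 | 0.0464 |
| γ = −4, equal thirds | 0.0026 | 0.0109 | 0.0456 |

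The value .4 gives nearly flat levels. The value −4 matches both interim levels to within 0.0001 but not the final one. Lan-DeMets O'Brien-Fleming spending (0.0002/0.0128/0.0460) and the classical O'Brien-Fleming bound (0.0006/0.0148/0.0449) do not fit either. Adding a binding futility bound to γ = −4 gives final levels from 0.0467 to 0.0584, and such designs are not symmetric. No variant tried returns all three printed levels.

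**3. Type I error of the printed levels.** On the 650 scale the increments are 0.0026 + 0.0104 + 0.0378 = 0.0508, or 0.0254 in one direction. With 446 + 130 = 576 as full information the total is 0.0496. With the interim levels kept, the final level that closes at 0.05 is 0.0455 on 650 and 0.0469 on 576. It is 0.0464 if look 2 holds 74.4% of the information (look 1 at 33.8%).

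**4. Sidedness of the sample size.** G1 cites a textbook chapter but prints no formula. A log-ratio formula, which is an inference, was tried at one-sided 0.05 and 80% power: (1.645 + 0.842)² = 6.183, using unrounded quantiles.

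- Sensitivity, true value 95% in both arms, 90% as the limit: 6.183 × 2(0.05/0.95)/[ln(0.90/0.95)]² = 6.183 × 0.10526/0.002923 = 222.6, so 223.
- Specificity 65% v 85%, so false-positive rates 35% v 15%: 6.183 × (0.65/0.35 + 0.85/0.15)/[ln(0.15/0.35)]² = 6.183 × 7.524/0.7179 = 64.8, so 65.

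Both planned sizes are reproduced. At two-sided 0.05 the factor is (1.960 + 0.842)² = 7.849, which gives 283 and 83.

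**5. Power under the printed rule.** If the sizes are one-sided, the expected final statistic is 1.645 + 0.842 = 2.487. A single test at two-sided 0.05 would have power Φ(2.487 − 1.960) = Φ(0.527) ≈ 70.1%. With the three printed levels, the recursion on the 650 scale gives 69.6%. Had the sizes been two-sided, the same rule would give 79.6%. The interim looks therefore cost about half a point, and the rest of the shortfall is sidedness.

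**The case against.** The strongest reply is that the rule can still be applied. Three thresholds are printed, G2 says the looks test the surveillance null hypotheses, and it names the primary tests. Few readers would run a survival test because of a stray phrase. That stands as to practical risk, but the phrase is complete and legible and should not remain in the decision rule.

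The .4 may be -4 damaged in typing or text extraction. That also stands, so the parameter is a matter to verify against the source calculation. It does not explain the final 0.0464, because -4 gives 0.0455 on the accrual scale.

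A reader might infer that the trial overspends its type I error and that 0.0464 must become 0.0455. The documents do not support this. The 0.0508 needs both a two-sided 0.05 and information proportional to 650 accrued, and the plan states no information scale. On 576 the spend is below 0.05, and against one-sided 0.05 there is no excess.

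A reader might also infer that one set of levels cannot serve both tests because they draw on different patients. That would require the neoplastic share to shift between looks, and nothing in the documents points to such a shift. It is a reason to state the information scale, not a demonstrated error.

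**Conclusion.** The paragraph is internally inconsistent and should be corrected. Three points rest on the text and direct calculation: the endpoint is not in the trial, .4 as it reads gives neither the printed levels nor the described shape, and the beta-spending label has no futility bound to refer to.

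The sidedness mismatch is probable rather than certain. It rests on an inferred formula and on reading 90% as the inferiority limit for sensitivity, but two separate sizes are reproduced. On that basis power is about 69.6% per test at the planned 223 and 65 per arm. Sensitivity could do better: 80% of 650 is 520 neoplastic patients, above 446. Specificity could not, because a neoplastic share above 80% leaves fewer than 130 benign patients.

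Type I error inflation is not shown.

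**What to change.** In G2:

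1. Replace the reference to overall survival with the non-inferiority test of sensitivity and the superiority test of specificity.
2. Check the spending parameter, including its sign, against the original calculation and label it alpha spending. Delete the beta-spending label unless a futility bound was intended; in that case print the bound and reconsider the word symmetric.
3. State whether 0.05 is one-sided or two-sided, in G1 and G2 alike, and state the information scale.
4. Derive the levels from the stated spending function, using the neoplastic count for sensitivity and the benign count for specificity at each look.
5. If the two-sided levels are kept, restate the power in G1 (about 69.6% per test if the sizes are one-sided). If one-sided 0.05 was intended, re-derive the levels on that basis.

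Replacing 0.0464 by 0.0455 should not be presented as a required correction. The cost is one paragraph in G2 and a sentence in G1, with no change in sample size.
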